6.2.5 Prior Radiation Therapy

Number and percentage of subjects who previously received any radiation therapy for the treatment of primary cancer, area radiated, and reason for radiation therapy will be summarized by cohort and overall for FAS and RES.

6.2.6 Prior Procedures for Primary Cancer and Concomitant Procedures

Number and percentage of subjects who had previously undergone any surgery or procedures for the treatment of primary cancer will be summarized by cohort and overall for FAS and RES.

Number and percentage of subjects who had undergone any on-study surgery or procedures will be summarized by cohort and overall for FAS and RES.

6.2.7 Previous and Concomitant Medications

Previous medications will be summarized by therapeutic subgroup (ATC 2nd level), chemical subgroup (ATC 4th level) and preferred WHO name by cohort and overall for the SAF.

As with previous medication, concomitant medications will be summarized by therapeutic subgroup (ATC 2nd level) and chemical subgroup (ATC 4th level) and preferred WHO name by cohort and overall for the SAF. Subjects taking the same medication multiple times will be counted once per medication and investigational period. A medication which can be classified into several chemical and/or therapeutic subgroups is presented in all chemical and therapeutic subgroups. All previous and concomitant medications will be coded by indication-specific ATC.

6.2.8 Previous and Concomitant Non-Medication Therapy

Subjects with previous and concomitant non-medication therapy and its reason for use will be provided in the listing.

6.2.9 New Anti-Cancer Therapy

Number and percentage of subjects receive any new anti-cancer therapy will be presented. Types of anti-cancer therapy and the reason for starting the new anti-cancer therapy will be summarized by cohort and overall for SAF.

6.2.10 New Radiation Therapy

Number and percentage of subjects who receive any subsequent radiation therapy will be presented. Types of radiation therapy and the reason for starting the new radiation therapy will be summarized by cohort and overall for SAF.

6.3 Study Drugs Exposure and Compliance

6.3.1 Cohorts 1 to 8

The following information of drug exposure will be presented by cohort and overall for the SAF:

- Descriptive statistics for duration of exposure, number of cycles, cumulative dose, planned dose intensity, dose intensity and relative dose intensity.
- Number and percentage of subjects with dose adjustment and reason for dose adjustment, dose reduction, and dose interruption. Dose reduction is defined as a dose given on a planned dosing day that is lower than the subject's initial dose of enfortumab vedotin. Dose interruption is defined as zero dose given on a planned dosing day with dosing resumed later.
- Duration of exposures will also be categorized according to the following categories, number and percentage of subjects in each categories will be summarized.
 - < 1 month
 - ≥ 1 and < 3 months
 - ≥ 3 and < 6 months
 - ≥ 6 months
 - Unknown

6.3.2 Cohort 9

The exposure analysis will be summarized by enfortumab vedotin, pembrolizumab and any drug for the SAF.

- Enfortumab vedotin: descriptive statistics for duration of exposure, number of cycles, cumulative dose, planned dose intensity, dose intensity and relative dose intensity. Number and percentage of subjects with dose adjustment and reason for dose adjustment, dose reduction, and dose interruption.
- Pembrolizumab: descriptive statistics for duration of exposure, number of cycles and cumulative dose. Number and percentage of subjects with dose interruption and reason for dose interruption.
- Any drug: descriptive statistics for duration of exposure and number of cycles
- Duration of exposures for enfortumab vedotin, pembrolizumab and any drug will also be categorized according to the following categories, number and percentage of subjects in each categories will be summarized.
 - < 1 month
 - ≥ 1 and < 3 months
 - ≥ 3 and < 6 months
 - ≥ 6 months and < 12 months
 - ≥ 12 months
 - Unknown

6.4 Analysis of Efficacy

Efficacy analysis will be conducted on the RES and FAS. RES will be the primary analysis population for response related endpoint, FAS will be the primary analysis population for PFS and OS.

6.4.1 Analysis of Primary Efficacy Endpoint

6.4.1.1 Primary Analysis for Primary Efficacy Endpoint

Confirmed ORR per RECIST Version 1.1 by investigator assessment will be calculated for each cohort. The corresponding 95% confidence interval will be constructed using the Clopper-Person method. The primary analysis set for confirmed ORR is the RES per investigator assessment.

ORR based on BOR regardless of the confirmation will also be calculated to evaluate the impact on ORR due to missing of confirmatory scans or PD after the initial response.

6.4.2 Analysis of Secondary Efficacy Endpoints

6.4.2.1 DOR per Investigator Assessment

DOR per RECIST Version 1.1 by investigator assessment will be summarized for subjects with confirmed CR or PR per investigator assessment in RES. Number and percentage of subjects with event and each event type (death, PD), censoring and each censoring type (no event, start new anti-cancer treatment before PD or death) will be summarized. DOR will be

analyzed using Kaplan-Meier methodology and Kaplan-Meier plots will be provided. The median, first quartile, third quartile and the corresponding two-sided 95% CIs will be calculated. The DOR rate at months 6, 12, 24, 36 will be summarized along with the corresponding 95% CI if applicable.

6.4.2.2 DCR per Investigator Assessment

DCR per RECIST Version 1.1 by investigator assessment will be calculated for each cohort. The corresponding 95% confidence interval will be constructed using the Clopper-Person method. The primary analysis set for DCR is the RES per investigator assessment.

DCR based on BOR regardless of the confirmation will also be calculated to evaluate the impact on DCR due to missing of confirmatory scans or PD after initial response.

6.4.2.3 PFS per Investigator Assessment

PFS per RECIST Version 1.1 by investigator assessment will be summarized for each cohort in the FAS. Number and percentage of subjects with an event and each event type (death, PD), censoring and each censoring type (no event, start new anti-cancer treatment before PD or death) will be summarized. PFS will be analyzed using Kaplan-Meier methodology and Kaplan-Meier plots will be provided. The median, first quartile, third quartile and the corresponding two-sided 95% CIs will be calculated. The PFS rate at months 6, 12, 24 and 36 will be summarized along with the corresponding 95% CI if applicable.

6.4.2.4 OS

OS will be summarized for each cohort in the FAS. Number of subjects with event and censoring will be summarized. OS will be analyzed using Kaplan-Meier methodology and Kaplan-Meier plots will be provided. The median, first quartile, third quartile and the corresponding two-sided 95% CIs will be calculated. The OS rate at months 6, 12, 24, 36 will be summarized along with the corresponding 95% CI if applicable.

6.4.2.5 BOR per Investigator Assessment

BOR with confirmation per RECIST Version 1.1 by investigator assessment will be summarized by cohort in RES. The number and percentage of subjects in each category will be presented.

BOR regardless of confirmation per RECIST Version 1.1 by investigator assessment will be summarized in the same way.

6.4.2.6 SOD

The maximum percent reduction in SOD from baseline per RECIST Version 1.1 by investigator assessment will be summarized using descriptive statistics by responder (confirmed CR or PR), SD and PD for each cohort. Maximum percent reduction in SOD from baseline will also be presented graphically in waterfall plot.

6.4.3 Analysis of Exploratory Endpoints

6.4.3.1 TTR per Investigator Assessment

TTR per investigator will be summarized with descriptive statistics by cohort for subjects achieving a confirmed CR or PR per RECIST Version 1.1 by investigator assessment in RES.

6.4.3.2 Endpoints per RECIST Version 1.1 by BICR

For cohorts with imaging scans read by BICR as defined in Section 5.3.2, confirmed ORR per BICR, DOR per BICR, DCR per BICR, PFS per BICR, BOR per BICR and TTR per BICR will be analyzed in the same way as the corresponding endpoints per investigator assessment as described in Sections 6.4.1 and 6.4.2.

Analyses based on RES population will require subjects to have measurable disease at baseline per BICR.

6.4.3.3 Endpoints per iRECIST by Investigator Assessment

For cohort 9 as defined in Section 5.3.3, confirmed iORR, iDOR, iDCR and iPFS per iRECIST as assessed by investigator will be analyzed in the same way as the corresponding endpoints per investigator assessment as described in Sections 6.4.1 and 6.4.2.

6.4.3.4 Biomarkers

For each cohort, baseline Nectin-4 IHC H-score will be summarized using mean, standard deviation, minimum, maximum, median, 25th percentile and 75th percentile. An exploratory analysis of assessing baseline IHC H-score with clinical outcomes may be conducted.

For each cohort, baseline PD-L1 results will be summarized by PD-L1 low and PD-L1 high according to the categories listed in the table below:

Table 2 PD-L1 Categorization for Each Cohort

Cohort	Cancer Type	PD-L1 Low	PD-L1 High
1	HR+/HER2- breast cancer	CPS < 1	CPS ≥ 1
2	TNBC	CPS < 10	CPS ≥ 10
3	Squamous NSCLC	TPS < 1%	TPS ≥ 1%
4	Non-squamous NSCLC	TPS < 1%	TPS ≥ 1%
5	Head and neck cancer	CPS < 1	CPS ≥ 1
7	Gastric adenocarcinoma or EAC or GEJ adenocarcinoma	CPS < 1	CPS ≥ 1
8	ESCC	CPS < 10	CPS ≥ 10
9	HNSCC	CPS < 1	CPS ≥ 1

An exploratory assessment of PD-L1 CPS or TPS with clinical outcomes may be conducted.

Summary statistics and exploratory assessments of Nectin-4 or PD-L1 expression with clinical outcome for combined cohorts may be performed and will be described in a separate biomarker analysis plan.

Additional biomarkers may be evaluated to explore effects on anti-tumor activity and safety of the study drug and will be described in a separate biomarker analysis plan.

6.4.3.5 Incidence of Antitherapeutic Antibodies

The number and percentage of subjects with positive postbaseline ATA will be tabulated by baseline ATA status for each cohort and overall for FAS.

6.4.3.6 EQ-5D-5L (for cohorts 1 to 8 only)

EQ-5D-5L will be summarized at each visit by cohort and overall for the FAS. Number and percentage of subjects in each level of 5 dimensions (mobility, self-care, usual activities, pain/discomfort and anxiety/depression) will be presented. A stacked column chart of the distribution of response to each dimension will be presented by visit, cohort and overall for FAS.

EQ-5D-5L utility index score and VAS will be summarized at each visit by cohort and overall for the FAS using descriptive statistics (mean, standard deviation, minimum, maximum and median). Additionally, a within-subject change will be calculated as the postbaseline score minus the baseline score and summarized in the same way.

The completion rate and compliance rate of EQ-5D-5L will be summarized at each visit by cohort and overall.

6.4.3.7 Global Pain Assessment

Global pain assessment score will be summarized at each visit by cohort and overall for the FAS using descriptive statistics. Additionally, a within-subject change will be calculated as the postbaseline score minus the baseline score and summarized in the same way. A line graph of median score together with 25th percentile and 75th percentile over time will be produced by cohort and overall.

The completion rate and compliance rate of global pain assessment will be summarized at each visit by cohort and overall.

6.4.3.8 EORTC QLQ H&N43 (for cohort 9 only)

The symptom scores will be summarized at each visit for the FAS using descriptive statistics (mean, standard deviation, minimum, maximum and median). Additionally, a within-subject change will be calculated as the postbaseline score minus the baseline score and summarized in the same way. The scoring algorithm is described in Appendix 4.

The completion rate and compliance rate of EORTC QLQ H&N43 will be summarized at each visit.

6.4.3.9 PRO-CTCAE (for cohort 9 only)

The assessment of fatigue and diarrhea symptoms will be summarized at each visit for the FAS. Number and percentage of subjects in each level of 3 questions will be presented. A stacked column chart of the distribution of response to each question will be presented by visit for FAS.

The completion rate and compliance rate of PRO-CTCAE will be summarized at each visit.

6.4.3.10 FACT-G (for cohort 9 only)

The response of GP5 question will be summarized at each visit for the FAS. Number and percentage of subjects in each level (Not at all, A little bit, Somewhat, Quite a bit, Very much) will be presented. A stacked chart of the distribution of response will be presented by visit for FAS.

The completion rate and compliance rate of FACT-G will be summarized at each visit.

6.4.4 Subgroup Analysis for Efficacy Endpoints

Exploratory analysis for selected efficacy endpoints per RECIST Version 1.1 (e.g., ORR, DCR, PFS, OS) may be conducted on subgroups based on demographic and baseline characteristics, disease history, and prior anti-cancer therapy when sufficient data are available, including but not limited to age, sex, race, region, baseline ECOG PS, baseline hemoglobin, anatomic staging at baseline, prior lines of therapy, prior lines of therapy in metastatic setting, prior use of CPI treatment, prior use of platinum based treatment, prior use of taxane, prior use of fluoropyrimidine therapy, prior use of targeted therapy, best response to prior anti-cancer therapy, best response to selected subtype of prior anti-cancer therapy if applicable. For cohort 9, subgroup analysis may be also conducted based on PD-L1 central testing results and time since prior radiation therapy.

6.5 Analysis of Safety

All analysis of safety will be presented by cohort and overall for the SAF, unless specified otherwise.

6.5.1 Adverse Events

All adverse events recorded on treatment including within 30 days from the last study treatment, or within 90 days from the last study treatment for SAEs in Cohort 9 will be summarized.

Summaries and listings of SAEs include SAEs upgraded by the sponsor based on review of the Sponsor's list of Always Serious terms or the important medical event process if any upgrade was done.

The coding dictionary for this study will be MedDRA. It will be used to summarize AEs by SOC and PT. AEs will be graded using National Cancer Institute's Common Terminology Criteria for AEs (NCI-CTCAE).

The definition of TEAEs leading to treatment discontinuation, TEAEs leading to interruption of treatment and TEAEs leading to dose reduction is listed below. The rules will be followed in the applicable TEAE analyses.

- TEAEs leading to permanent discontinuation of study drug is defined as TEAEs leading to withdrawal of any study drug (enfortumab vedotin or pembrolizumab) in Cohorts 1-9. TEAEs leading to permanent discontinuation of enfortumab vedotin is defined as TEAEs leading to withdrawal of enfortumab vedotin in Cohort 9. TEAEs

leading to permanent discontinuation of pembrolizumab is defined as TEAEs leading to withdrawal of pembrolizumab in Cohort 9.

- TEAEs leading to dose interruption is defined as TEAEs leading to interruption of any study drug (enfortumab vedotin or pembrolizumab) in Cohorts 1-9. TEAEs leading to interruption of enfortumab vedotin is defined as TEAEs leading to interruption of enfortumab vedotin in Cohort 9. TEAEs leading to interruption of pembrolizumab is defined as TEAEs leading to interruption of pembrolizumab in Cohort 9.
- TEAEs leading to dose reduction is defined as TEAEs leading to reduction of enfortumab vedotin in Cohorts 1-9. Pembrolizumab reduction is not allowed.

An overview table to report the number and percentage of subjects and another overview table to report number of events and events adjusted by patient year of drug exposure will include the following details by cohort and overall:

- Number and percentage of subjects with TEAEs,
- Number and percentage of subjects with drug-related TEAEs,
- Number and percentage of subjects with serious TEAEs,
- Number and percentage of subjects with serious drug-related TEAEs,
- Number and percentage of subjects with TEAEs leading to permanent discontinuation of study drug,
- Number and percentage of subjects with TEAEs leading to permanent discontinuation of enfortumab vedotin,
- Number and percentage of subjects with TEAEs leading to permanent discontinuation of pembrolizumab,
- Number and percentage of subjects with drug-related TEAEs leading to permanent discontinuation of study drug,
- Number and percentage of subjects with drug-related TEAEs leading to permanent discontinuation of enfortumab vedotin,
- Number and percentage of subjects with drug-related TEAEs leading to permanent discontinuation of pembrolizumab,
- Number and percentage of subjects with TEAEs leading to dose reduction,
- Number and percentage of subjects with drug-related TEAEs leading to dose reduction,
- Number and percentage of subjects with TEAEs leading to dose interruption,
- Number and percentage of subjects with TEAEs leading to interruption of enfortumab vedotin,
- Number and percentage of subjects with TEAEs leading to interruption of pembrolizumab,
- Number and percentage of subjects with drug-related TEAEs leading to dose interruption,
- Number and percentage of subjects with drug-related TEAEs leading to interruption of enfortumab vedotin,

- Number and percentage of subjects with drug-related TEAEs leading to interruption of pembrolizumab,
- Number and percentage of subjects with grade 3 or higher TEAEs,
- Number and percentage of subjects with grade 3 or higher drug-related TEAEs,
- Number and percentage of subjects with TEAEs leading to death,
- Number and percentage of subjects with drug-related TEAEs leading to death,
- Number and percentage of subjects with TEAEs leading to death excluding disease progression,
- Number and percentage of subjects with drug-related TEAEs leading to death excluding disease progression, and
- Number of deaths.

The number and percentage of subjects with TEAEs, as classified by SOC and PT will be summarized by cohort and overall. Summaries will be provided for the following:

- TEAEs
- drug related TEAEs,
- serious TEAEs,
- drug related serious TEAEs,
- TEAEs leading to permanent discontinuation of study drug,
- TEAEs leading to permanent discontinuation of enfortumab vedotin,
- TEAEs leading to permanent discontinuation of pembrolizumab,
- drug related TEAEs leading to permanent discontinuation of study drug,
- drug related TEAEs leading to permanent discontinuation of enfortumab vedotin,
- drug related TEAEs leading to permanent discontinuation of pembrolizumab,
- TEAEs leading to dose reduction,
- drug-related TEAEs leading to dose reduction,
- TEAEs leading to dose interruption,
- TEAEs leading to interruption of enfortumab vedotin,
- TEAEs leading to interruption of pembrolizumab,
- drug-related TEAEs leading to dose interruption,
- drug-related TEAEs leading to interruption of enfortumab vedotin,
- drug-related TEAEs leading to interruption of pembrolizumab,
- grade 3 or higher TEAEs,
- grade 3 or higher drug-related TEAEs,
- TEAEs leading to death,
- drug-related TEAEs leading to death,
- TEAEs leading to death excluding disease progression,
- drug-related TEAEs leading to death excluding disease progression,
- Common TEAE that equal to or exceed a threshold of 5% in any cohort (excluding serious AEs)

The number and percentage of subjects with TEAEs, as classified by PT only, will be summarized for each cohort and overall for the following:

- TEAEs,
- drug related TEAEs,
- serious TEAEs,
- drug related serious TEAEs,
- grade 3 or higher TEAEs,
- grade 3 or higher drug-related TEAEs,
- TEAEs leading to permanent discontinuation of study drug,
- TEAEs leading to permanent discontinuation of enfortumab vedotin,
- TEAEs leading to permanent discontinuation of pembrolizumab,
- drug related TEAEs leading to permanent discontinuation of study drug,
- drug related TEAEs leading to permanent discontinuation of enfortumab vedotin,
- drug related TEAEs leading to permanent discontinuation of pembrolizumab,
- TEAEs leading to dose reduction,
- drug-related TEAEs leading to dose reduction,
- TEAEs leading to dose interruption,
- TEAEs leading to interruption of enfortumab vedotin,
- TEAEs leading to interruption of pembrolizumab,
- drug-related TEAEs leading to dose interruption,
- drug-related TEAEs leading to interruption of enfortumab vedotin,
- drug-related TEAEs leading to interruption of pembrolizumab,
- TEAEs leading to death,
- drug-related TEAEs leading to death

AE summary tables will include subject counts as opposed to AE counts. If a subject experiences more than one episode of a particular AE, the subject will be counted only once for that event. If a subject has more than one AE that code to the same preferred term, the subject will be counted only once for that preferred term. Similarly, if a subject has more than one AE within a body system, the subject will be counted only once for that body system.

The number and percentage of subjects with TEAEs, as classified by SOC and PT will be summarized by NCI-CTCAE grade and by relationship to study drug. If a subject has multiple TEAEs with the same SOC or PT, but with differing CTCAE grade or relationship, then the subject will be counted once with the worst nonmissing CTCAE grade and the highest degree of relationship. If CTCAE grade is missing for all episodes of the event, the subject will be counted under missing CTCAE grade. If relationship is missing for an adverse event, it's considered to have the highest degree of relationship.

The number and percentage of subjects with treatment-emergent AESIs, as classified by AESI category and PT, will be summarized for each cohort and overall for the following:

- Treatment-emergent AESIs,
- Drug-related treatment-emergent AESIs,
- Treatment-emergent AESIs by NCI-CTCAE grade,
- Drug-related treatment-emergent AESIs by NCI-CTCAE grade,

- Serious treatment-emergent AESIs,
- Treatment-emergent AESIs leading to permanent discontinuation of study drug,
- Treatment-emergent AESIs leading to permanent discontinuation of enfortumab vedotin,
- Treatment-emergent AESIs leading to permanent discontinuation of pembrolizumab,
- Treatment-emergent AESIs leading to dose reduction,
- Treatment-emergent AESIs leading to dose interruption,
- Treatment-emergent AESIs leading to interruption of enfortumab vedotin,
- Treatment-emergent AESIs leading to interruption of pembrolizumab

For selected AESI, time to first onset of AESI, time to first onset of specific grade of AESI (e.g., grade 3 or higher, grade 2 or higher) and time to resolution will be summarized by descriptive statistics by AESI category for each cohort and overall. Time to onset will be summarized at the subject level. Time to resolution will be summarized at the event level.

For other AEs of risk for EV, it will be summarized in the same way as AESI.

For AEOSI, the following tables will be generated:

- Adverse event summary for AEOSI
- Adverse event summary by AEOSI category
- Participants with adverse events of special interest by AEOSI category and preferred term
- Participants with adverse events of special interest by AEOSI category, preferred term, and maximum toxicity grade
- Time to onset of AEOSI
- Summary of concomitant corticosteroid use for AEOSI
- Participants with AEOSI by outcome

All AEs, SAEs, deaths, withdrawals due to adverse events, AESI, other AEs of risk for EV and AEOSI will be displayed in listings.

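### SAP 6.5.1 defines TEAEs leading to discontinuation or interruption of enfortumab vedotin for cohort 9 only but lists them in all-cohort tables on the whole SAF, so a literal reading gives an overall percentage that is too low

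*SAP*

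**What the plan says.** The default for safety output is in SAP 6.5: "All analysis of safety will be presented by cohort and overall for the SAF, unless specified otherwise". SAP 4.3 makes the SAF everyone who received any study drug.

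SAP 6.5.1 then defines three kinds of action taken because of a TEAE:

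- **Discontinuation.** The study-drug category covers "withdrawal of any study drug (enfortumab vedotin or pembrolizumab) in Cohorts 1-9". The drug-specific category is narrower: "TEAEs leading to permanent discontinuation of enfortumab vedotin is defined as TEAEs leading to withdrawal of enfortumab vedotin in Cohort 9". Pembrolizumab has a parallel cohort 9 definition.
- **Interruption.** This has the same structure: "TEAEs leading to interruption of enfortumab vedotin is defined as TEAEs leading to interruption of enfortumab vedotin in Cohort 9".
- **Dose reduction.** This is wider: "TEAEs leading to dose reduction is defined as TEAEs leading to reduction of enfortumab vedotin in Cohorts 1-9".

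The definitions are introduced with the statement "The rules will be followed in the applicable TEAE analyses".

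The overview tables, presented for each cohort and for all cohorts together, include "Number and percentage of subjects with TEAEs leading to permanent discontinuation of enfortumab vedotin", the matching interruption row, the drug-related versions and the pembrolizumab rows. The SOC/PT and PT tables carry the same categories. The AESI tables include, for example, "Treatment-emergent AESIs leading to interruption of enfortumab vedotin", and the other AEs of risk are to be handled in the same way as AESIs. A second overview table reports events adjusted for patient-years of exposure.

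**The concern.** Enfortumab vedotin is given in every cohort and is the only study drug in cohorts 1 to 8. A definition that stops at cohort 9 therefore leaves out most of the people exposed, while the table instructions still ask for all cohorts and a pooled column. Dose reduction of the same drug is defined for cohorts 1 to 9 in the same list, and no reason is given for the difference.

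A programmer who follows the text literally would show zero enfortumab vedotin discontinuations in each monotherapy cohort, beside a non-zero study-drug row describing the same drug. The overall cell would have a cohort 9 numerator and an all-cohort denominator. The overall pembrolizumab cell would divide by subjects who never received pembrolizumab.

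Safety and tolerability are a secondary objective, and stopping or holding the drug because of an adverse event is a main tolerability result. The pooled column will be produced: SAP 6.8 brings in non-efficacy data from all cohorts at the primary analysis of the last enrolling cohort.

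**Working it through.** **Inputs**

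- Planned size: about 320 subjects in 8 cohorts of about 40 (Protocol 1.1). Check: cohorts 1, 2, 3, 4, 5, 7, 8 and 9, with cohort 6 reallocated, give 8 × 40 = 320, which agrees.
- Cohort 9: 40 planned (SAP 3).
- Cohort 5: 46 enrolled (Protocol 2.4.1). Other cohorts may end below 40 after the interim analysis (SAP 3).
- Illustrative enfortumab vedotin discontinuation rate: 126/680 = 18.5%, from the pooled 1.25 mg/kg monotherapy population (Protocol 2.2.1.3). It is not a rate from this trial.

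The documents state no rate or denominator for these rows, so there is no figure of the plan's own to reproduce beyond the 320.

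**Formula.** Let n and r be the size and event rate of each cohort.

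- All-cohort percentage = Σ(n × r) / N, with N the whole SAF.
- Literal-reading percentage = (n₉ × r₉) / N.
- Understatement factor = Σ(n × r) / (n₉ × r₉). This reduces to N / n₉ only when r is the same in every cohort.

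**Planned sizes, equal rates.** 0.185 × 320 = 59.2 subjects, and 59.2/320 = 18.5%. The literal reading gives 0.185 × 40 = 7.4, and 7.4/320 = 2.3%. The factor is 320/40 = 8.0.

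**Other assumptions**

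| Assumed sizes and rates | Calculation | Factor |
|---|---|---|
| Cohort 5 at 46, others 40, equal rates | 326/40 | 8.15 |
| Cohort 5 at 46, other six monotherapy cohorts 20, equal rates | 206/40 | 5.15 |
| All seven monotherapy cohorts 20, equal rates | 180/40 | 4.5 |
| Cohort 9 at 20, cohort 5 at 46, others 40, equal rates | 306/20 | 15.3 |
| 40 each, cohort 9 rate 1.5 times the monotherapy rate | (280 + 60)/60 | 5.7 |
| 40 each, cohort 9 rate 2 times | (280 + 80)/80 | 4.5 |
| 40 each, cohort 9 rate 0.5 times | (280 + 20)/20 | 15.0 |
| Cohort 9 rate 2 times, cohort 5 at 46, other six at 20 | (166 + 80)/80 | 3.1 |

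If the overall cell uses cohort 9 as its denominator, 7.4/40 = 18.5% and nothing is understated.

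**Pembrolizumab rows.** All events are in cohort 9, so dividing by the whole SAF dilutes the percentage by N / n₉ whatever the rate. With the 12% discontinuation quoted for single-agent pembrolizumab in another trial (Protocol 2.5.1) as an illustration, 0.12 × 40 = 4.8. That is 12% of cohort 9 but 4.8/320 = 1.5% of the SAF.

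**Exposure-adjusted overview.** The same mismatch arises, with cohort 9 events over all-cohort patient-years. Its size depends on exposure by cohort, which the documents do not give.

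**The case against.** The best defence is that nobody intended a whole-SAF denominator. The SAF rule allows exceptions, the definitions name cohort 9, and the rules are to be followed only where applicable. Splitting by drug matters only where two drugs are given, and the version 3.0 entry in SAP 7 describes the change as adding TEAE analyses for cohort 9. Table layouts are left to separate specifications (SAP 6.1). A cohort 9-only display is therefore a plausible intent.

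That limits what can be claimed but does not remove the gap. Elsewhere the SAP labels restricted outputs explicitly: sections 6.2.4, 6.4.3.6 and 6.4.3.8 to 6.4.3.10 and the laboratory table in 5.4 all do so, and 6.5.2.1 states its own denominator. These rows carry no such label.

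A reader might go further and infer that monotherapy discontinuation data are lost. They are not. In cohorts 1 to 8 the study-drug rows are the enfortumab vedotin rows, and cohort 9 has its own row, so the study-wide count follows by addition. What is missing is a row that gives it directly: the study-drug row in cohort 9 also counts pembrolizumab-only withdrawals, after which Protocol 8.1 allows enfortumab vedotin to continue.

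It is also fair that pooling monotherapy with a combination on a different schedule has limited meaning, and that the cohort columns are the informative ones.

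**Conclusion.** The concern holds as a defect in the table rules. Followed as written, the overall enfortumab vedotin and pembrolizumab percentages, and the exposure-adjusted rates, pair a cohort 9 numerator with an all-cohort denominator. The monotherapy columns then show zero for a drug those subjects received.

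A reader might take the understatement to be eight-fold as a fact. The documents do not support that. Eight-fold requires the whole-SAF denominator, equal event rates in monotherapy and combination cohorts, and 40 treated in each of 8 cohorts. Under the other sizes and rates tried for enfortumab vedotin the factor runs from about 3 to 15, and it is 1 if cohort 9 is the denominator. The 18.5% and 12% used above come from outside this trial and serve only as illustrations.

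The primary endpoint and the interim boundaries are not touched, and per-cohort tolerability can still be read from the tables.

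**What to change.** In SAP 6.5.1, choose one of two options for enfortumab vedotin:

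1. Define the discontinuation and interruption categories for cohorts 1 to 9, matching the dose-reduction definition.
2. Keep the cohort 9 definitions, label the rows cohort 9 only, use the cohort 9 SAF as N, and drop the overall column for them.

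Under either option, show the pembrolizumab-specific rows for cohort 9 only, with the cohort 9 SAF as denominator and no overall column.

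Apply the choice consistently to the drug-related rows, the SOC/PT and PT tables, the exposure-adjusted overview (with cohort 9 exposure as the denominator wherever the row is cohort 9 only) and the AESI tables.

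The cost is a line of SAP wording and one derivation flag, with no new data. Under the first option the enfortumab vedotin row repeats the study-drug row in cohorts 1 to 8. Under the second, a study-wide enfortumab vedotin figure still has to be added up by hand.
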